IRB Study Number: 20160951
Version #11; 7-18-2022

**RANDOMIZED, DOUBLE-BLINDED, CONTROLLED
TRIAL OF EARLY-INTERVENTION TENS
FOR THE REDUCTION OF THE PREVALENCE AND
SEVERITY OF CHRONIC NEUROPATHIC PAIN
DURING THE FIRST YEAR AFTER
SPINAL CORD INJURY**

IRB Number: 20160951
Protocol Version Number: 0.11
Protocol Version Date: 7/18/2022
PI Name: [name]
NCT Number: NCT03267810

1) Protocol Title

Randomized, double-blinded, controlled trial of early-intervention TENS for the reduction of the prevalence and severity of chronic neuropathic pain during the first year after spinal cord injury (SCI)

2) Objectives*

The primary objectives of our site-specific project are to test a non-invasive, non-pharmacologic, inexpensive intervention (i.e., transcutaneous electrical nerve stimulation; TENS) to prevent the development and reduce the severity of chronic neuropathic pain in the first year post-spinal cord injury (SCI) (Aim 1), and to increase the understanding of the time-course of the development of chronic neuropathic pain and the factors that increase the risk for neuropathic pain onset or worsening by longitudinally tracking pain symptoms, somatosensory function, and key injury-related and psychosocial factors during the first 12 months post-SCI (Aim 2).

Aim 1: Assess the effectiveness of preemptive/early-intervention TENS therapy to decrease the risk of developing chronic neuropathic pain, and to reduce the severity of neuropathic pain, following SCI.

Hypothesis 1a: Enhanced somatosensory stimulation using TENS within preserved dermatomes at or above the neurological level of injury will reduce the prevalence and severity of chronic neuropathic pain at 12 months post-injury when compared with neuropathic pain in those who receive Sham TENS.

Hypothesis 1b: Subjects for whom TENS effectively reduces evoked pain sensations (i.e., increased pain thresholds and/or decreased ratings of perceived intensity of noxious suprathreshold stimuli) at, and including three levels below, the level of injury after an 8-week TENS treatment protocol will be less likely to report chronic neuropathic pain

symptoms at 12 months post-injury than subjects for whom TENS does not reduce evoked pain sensations.

Aim 2: Evaluate demographic, psychological, and physiological characteristics that are potential risk factors for the development and severity of chronic neuropathic pain at 12 months post-injury.

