Modality	SCI		Nondisabled	
	ICC (95% CI)	# total test sites	ICC (95% CI)	# total test sites
Log MDT	0.84 (0.75-0.90)	56	0.63 (0.45-0.76)	58
Log VDT	0.90 (0.84-0.94)	67	0.86 (0.79-0.91)	80
Log CDT	0.90 (0.83-0.94)	55	0.68 (0.54-0.78)	80
Log WDT	0.95 (0.91-0.97)	50	0.70 (0.57-0.80)	79
CPT	0.50 (0.28-0.67)	56	0.49 (0.31-0.64)	80
HPT	0.50 (0.28-0.66)	62	0.68 (0.55-0.79)	79

MDT = mechanical detection threshold; VDT = vibration detection threshold; CDT = cool detection threshold; WDT = warm detection threshold; CPT = cold pain threshold; HPT = hot pain threshold

severity of chronic neuropathic pain symptoms, in participants with chronic SCI.^{6, 8, 74} **Figure 4** shows that, in test sites in body areas where neuropathic pain symptoms were present, lower pain thresholds (i.e., increased pain sensitivity) were associated with more severe neuropathic pain scores.

Thus, previous work by the study investigators demonstrates that the study is feasible and that they have the skills and tools necessary to perform the proposed study. Results from this body of work support the rationale of the proposed site-specific study.

Figure 4: Pain threshold is negatively related to severity of NeuP in those with SCI

Subjects with SCI and NeuP ($n = 22$) completed sensory testing at sites within the area affected by NeuP. Thresholds were also obtained in control subjects at the same test sites on the body and used to calculate z-scores for the thresholds obtained in those with SCI. Subjects with less loss of pain sensation (z-scores close to 0) had significantly higher NPSI scores than those with greater loss of pain sensation (higher z-scores).⁷⁴ (Z-scores reflect the degree to which thresholds in participants with SCI vary from the distribution of thresholds obtained in nondisabled control subjects, and allow for comparison of measures obtained at different locations on the body.)

4) Inclusion and Exclusion Criteria*

Inclusion criteria:

- Age ≥ 18 ;
- Traumatic spinal cord injury;
- Date of injury occurring within four months of study enrollment.

Exclusion criteria:

- More than four months since date of injury;
- Contraindications for the study intervention, transcutaneous electrical nerve stimulation (TENS),⁸⁸ including:
 - Implanted electronic device such as a pacemaker;
 - Cardiovascular problems;
 - Pregnancy;
 - Epilepsy;
 - Cancer;
- Persons with a spinal cord injury at the C2 level, as placement of TENS electrodes on the neck is not recommended;

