Safety endpoints include frequency and severity of adverse events and increased likelihood of developing chronic pain due to TENS treatment. Please see section 13: “Provisions to monitor the data to ensure the safety of subjects,” describes the monitoring of the safety endpoints.

[figure not shown]
9) Procedures Involved*

Overview:

The primary study design will be a randomized, double-blinded, controlled trial of early intervention TENS compared to Sham TENS, with longitudinal tracking of signs and symptoms of NeuP, as well as symptoms and severity of non-neuropathic pains, pain impact, and psychological function, for 12 months post-SCI. **Figure 5** diagrams the study procedures, subject flow, and assessment time points.

Patients will be eligible for recruitment into the study as soon as they have been admitted to the SCI inpatient rehabilitation unit at UM/JMH/Lynn Rehabilitation Center (see Section 21 for full recruitment procedures). Treatment TENS or Sham TENS sessions (see “Randomization procedures,” below) will be initiated within four months post-injury (with four weeks post-injury as the target, if feasible).

Figure 5: Timeline of subject participation and study procedures

* Note the above diagram depicts the anticipated average time course of study procedures across subjects. Due to varying times between injury and admission to/discharge from inpatient SCI rehabilitation, not all subjects will begin participation in the study precisely at the two-month post-injury timepoint.

Subjects will be enrolled and randomized regardless of whether they have NeuP symptoms at initial assessment. Because approximately 25% of SCI patients who report chronic neuropathic pain at 1 year post-injury had initial neuropathic pain symptoms at 1 month post- injury,²¹ initiating treatment at four weeks post-injury will capture approximately 75% of patients before their neuropathic pain symptoms manifest. In those patients who do have neuropathic pain symptoms at the baseline assessment, we will be able to test the ability of TENS to interfere with the transition from acute to chronic neuropathic pain, by comparing the decrease in severity of neuropathic pain symptoms from baseline to 12 months post-injury between the two study groups (Treatment TENS vs Sham TENS).

Once baseline assessments are completed, treatment will be administered twice a week, for 30 minutes each session, for 8 weeks.

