(a) *Assessment procedures*: **Table 2** lists measures that will be collected during full and abbreviated assessments, as well as before and after each TENS session. Full assessment sessions will occur at three time points: baseline (prior to treatment initiation); termination of the 8-week treatment protocol; and 12 months post-injury. The full assessment protocol will require approximately 180 minutes to complete and may be completed in multiple sessions due to participant availability. An abbreviated assessment protocol will be administered at the 4-week treatment time point (i.e., halfway through the full series of treatment sessions), and over the phone each month after treatment has ended, until the 12-month post-injury time point. The abbreviate assessment will require 30 minutes to complete. In addition, numerical ratings of pain and the Neuropathic Pain Symptom Inventory⁸⁹ will be assessed before and immediately after each 30-minute TENS session. (It is expected that, for most patients, pain ratings will be “0,” as many will not have developed neuropathic pain symptoms in the first few months after injury when TENS is being administered. Collection of this information is important in order to insure that TENS is not related to any increase in pain symptoms during treatment.) Adverse events/ side effects will also be captured at the end of each TENS session. The assessment schedule is depicted by the blue and yellow boxes at the bottom of **Figure 5**.

Table 2: List of assessment tools to be used

Assessment domain	Assessment	Full assessment	Abbreviated assessment	Treatment sessions
Pain classification	SCIP, and ISCPBDS2	X	X	
Pain intensity and symptoms	NRS for pain ISCPBDS2	X	X	X

	ISCIPEDES [“pain symptoms” subset]	X		
	NPSI	X	X	X
	sf-MPQ-2	X		
Maladaptive pain coping	PCS	X		
Sensory function	ASIA sensory scores*	X		
	QST	X		
Emotional function	PHQ-9*	X	X	
	SCI-QOL Resilience scale – short form *	X	X	
Treatments	Frequency, dose, effectiveness (from ISCIPEDES)	X	X	
Adverse events	Incidence and severity			X
Time required (minutes)		120	30	5

* measures/assessments that overlap with national database Form I/II

** assessments that will only be carried out at 12-months post-injury

(b) *Assessment tools:* Copies of all instruments to be used are uploaded within the eProst UM-IRB application for this study.

i. Pain classification:

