Based on a total sample size of 98 subjects, and an estimated 15% drop-out rate, we expect that approximately 82 subjects will complete the study (i.e., 41 subjects per treatment arm). Based on previous work,^{21, 59} we project that 60% of subjects in the Sham TENS (control) group will have at- or below-level neuropathic pain at the 12 month follow-up time point. Thus, with 41 subjects in each group, $\alpha = 0.05$, power of at least 80%, and an analysis based on a two-sided Z-test (for group difference in proportion of subjects with neuropathic pain) for *Hypothesis 1a*, we will be able to detect at least a 50% reduction in the rate of subjects with chronic neuropathic pain in the TENS treatment group compared to the Sham group at 12 months post-SCI (i.e., Sham TENS = 60% with neuropathic pain; Treatment TENS = 30% neuropathic pain).

For t-test analyses assessing differences between groups (Sham vs. Treatment) using continuous variables (e.g., NRS, NPSI), 41 subjects in each group will allow for detection of a medium-to-large effect size (i.e., Cohen's $d = 0.6$) with α set at 0.05 and power of 0.80. Paired correlations will also be used for additional analyses (*Aim 2*). For correlations within group ($n = 41$), with power set at 0.80 and $\alpha = 0.05$, we will be able to detect a medium-to-large effect size (i.e., Cohen's $f^2 = 0.20$), and we will be able to detect a small-to-medium effect size for across-group analyses ($n = 82$; Cohen's $f^2 = 0.10$).

Data analysis plan:

Descriptive evaluations of the data will be performed for all variables to check the integrity of the data and to verify the underlying assumptions of the statistical tests that are planned. If necessary, and as appropriate, data will be transformed prior to any parametric analyses, or non-parametric techniques will be used with untransformed data. Statistical analyses will use two-tailed tests and an a-priori α of 0.05.

In addition to direct tests of hypotheses (described in detail below), descriptive analyses and graphical representations (e.g., spaghetti plots) of data will be used to describe longitudinal

characteristics of clinical pain, somatosensory function, and other physical and psychological outcomes across the 12-month timeline of study participation.

Hypothesis 1a:

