symptoms at the 12 month post-injury time point. It is anticipated that those who show reduced sensitivity to noxious stimuli after TENS treatments will exhibit a lower risk for chronic neuropathic pain. A repeated measures regression analysis, including appropriate covariates (e.g., demographic and injury-related factors, concomitant treatments, amplitude setting of TENS treatments), will assess whether changes in evoked pain sensitivity will be a significant predictor of neuropathic pain at 12 months post-injury in the TENS treatment group.

Hypotheses 2a, 2b, and 2c:

Chi square analyses, t-tests, and correlations across all subjects (with TENS group assignment as a covariate) will be used to separately examine whether demographic variables (age and minority status), psychological characteristics (pain catastrophizing, depressive symptoms severity, and levels of resilience), and measures of evoked pain sensitivity (pain thresholds and ratings of suprathreshold noxious stimuli) measured at baseline can predict the presence and severity of chronic neuropathic pain at 12 months post-SCI. Separate sub-analyses will also be conducted with regard to the impact of these factors on pains with different diagnostic categories (nociceptive pain, neuropathic pain).

Data security / Quality control:

All research personnel will complete and maintain trainings regarding privacy and data security as required. All personnel will receive training regarding all study procedures as required for their role, as assigned and overseen by the PI, to insure data quality and integrity of the science.

Data for the study will be recorded on paper, using the most-updated and approved study forms. These paper documents will be stored in locked file cabinets in rooms 3.156 and 3.153B of the Christine E. Lynn Rehabilitation Center ([name]). This room is locked and is accessible only by those who have been given card access. These paper documents will be stored for at least 3 years after the final termination of the grant.

Data from the paper documents will be entered into a password protected electronic database that will receive periodic and thorough data quality checks through established procedures. This

electronic file will not contain any personally-identifiable information, and will be maintained for at least 3 years after the final termination of the grant.

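### Hypotheses 2b and 2c use baseline measures taken at varying times up to four months after injury, but time since injury is neither a covariate nor a stated time axis

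*Combined protocol and SAP*

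**What the plan says.** **Entry.** The inclusion criterion in section 4 is "Date of injury occurring within four months of study enrollment". Section 9 (Overview) states "Patients will be eligible for recruitment into the study as soon as they have been admitted to the SCI inpatient rehabilitation unit", so there is no minimum time since injury. Sessions "will be initiated within four months post-injury (with four weeks post-injury as the target, if feasible"). The note to Figure 5 acknowledges that "not all subjects will begin participation in the study precisely at the two-month post-injury timepoint".

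**Visits.** Under Assessment procedures in section 9, the baseline, treatment week 4 and end-of-treatment assessments are tied to entry and to the 8-week course. Calls then follow "over the phone each month after treatment has ended, until the 12-month post-injury time point". The end of follow-up is fixed on the injury clock, but the start is not.

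**Aim.** Section 2 sets out "to increase the understanding of the time-course of the development of chronic neuropathic pain", together with its risk factors, by tracking subjects through the first 12 months after SCI.

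**Analysis.** In section 11, longitudinal characteristics are to be described "across the 12-month timeline of study participation". For the baseline predictors of Hypotheses 2a to 2c (demographic, psychological and evoked-pain), the analysis sentence begins "Chi square analyses, t-tests, and correlations across all subjects (with TENS group assignment as a covariate) will be used to separately examine". TENS group is the only covariate named. Injury-related factors appear only as an example covariate for Hypothesis 1b, in an analysis limited to the TENS arm.

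**The concern.** The entry window overlaps the period in which the condition appears. Section 3 says that neuropathic pain after SCI often takes at least a few months to develop. Section 9 says that about 25% of those with chronic neuropathic pain at one year already had symptoms at one month. A baseline taken at four weeks will mostly precede pain, while one taken at four months may follow its onset.

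For Hypotheses 2b and 2c, catastrophizing, depressive symptoms, resilience and evoked-pain sensitivity are compared across subjects measured at different distances from injury. If these measures shift with time since injury, part of their spread reflects only the date of measurement. That is noise. If time of entry is also related to 12-month pain, it becomes confounding. Section 3 faults cross-sectional work for being unable to tell whether sensory dysfunction is a cause or a result of pain. Pooling early and late baselines without adjustment could bring part of that ambiguity back.

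For the time-course, a curve drawn by visit or by time in study would average subjects at different points after injury.

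**Working it through.** **1. The plan's own figure.** Section 11 states that n = 82 across groups gives power 0.80 for Cohen's f² = 0.10 at two-sided α = 0.05. The check is an F test of one predictor with noncentrality λ = f² × n = 0.10 × 82 = 8.2 on (1, 80) degrees of freedom. Power is 0.808, so the figure reproduces. The implied correlation is r = √(0.10/1.10) = 0.302.

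**2. Spread in time since injury.** The inputs are entry at the 4-week target or at the 4-month limit, an 8-week treatment course and a last assessment at month 12 after injury. With 30.44 days per month, 4 weeks = 0.92 months and 8 weeks = 1.84 months.

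| | Entry at 4 weeks | Entry at 4 months |
|---|---|---|
| Baseline (months after injury) | 0.92 | 4.00 |
| End of treatment | 0.92 + 1.84 = 2.76 | 4.00 + 1.84 = 5.84 |
| Observation to month 12 | 12 − 0.92 = 11.1 months | 12 − 4 = 8.0 months |

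Visits of the same name differ by up to 4.00 − 0.92 = 3.1 months. Four weeks is a target and not a floor, so the spread could be wider.

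**3. Who is observed prospectively in the early months.** The documents give no distribution of entry times. Assuming uniform entry between 4 weeks and 4 months, the share enrolled by month m is (m − 0.92)/(4 − 0.92). This gives 35% at month 2, 68% at month 3 and 100% at month 4. Entry concentrated around two months, as the Figure 5 note suggests, would raise the early shares.

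**4. If timing is pure noise (assumption).** Let entry timing explain a share R² of a predictor's variance and be unrelated to the outcome. The true correlation seen in the data shrinks to 0.302 × √(1 − R²). Power follows from step 1 with f² = r²/(1 − r²).

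| R² | Attenuated r | f² | Power at n = 82 |
|---|---|---|---|
| 0 | 0.302 | 0.100 | 81% |
| 0.10 | 0.286 | 0.089 | 76% |
| 0.20 | 0.270 | 0.078 | 71% |
| 0.30 | 0.252 | 0.068 | 65% |

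The correlation that the design can detect does not change. The correlation available to be detected shrinks.

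**5. If timing confounds (assumption).** Suppose a predictor has no association with the outcome given entry time, but entry time correlates a with the predictor and b with the outcome. The unadjusted correlation is then a × b. By the Fisher z approximation with √(82 − 3), the rejection rate at nominal 5% is:

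| a and b | a × b | Rejection rate |
|---|---|---|
| 0.2 and 0.2 | 0.04 | 6.5% |
| 0.3 and 0.3 | 0.09 | 13% |
| 0.4 and 0.4 | 0.16 | 30% |

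**6. Price of adjustment.** At a partial f² of 0.10 and n = 82, power is 0.8075 in a model with the predictor and TENS group. It is 0.8074 once time since injury is added.

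**The case against.** Several counter-arguments stand and limit the point.

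- **Pain before entry is not wholly unseen.** Section 9 records the onset of each pain condition through the ISCIPBDS2 and asks for average pain over the past 3 months. For a four-month entrant, that recall reaches back to about month 1. A reader might infer that early pain development is known only in early entrants, but the documents do not support that. The gap applies to quantitative sensory testing and psychological scores, which have no such recall.
- **The time axis is ambiguous, not shown to be wrong.** Section 11 fixes no axis. Nobody entering at one to four months participates for 12 months, so its 12-month timeline may well mean the post-injury year. Section 9 also speaks of tracking for 12 months after SCI. It would go too far to say that the plan commits to visit-based curves.
- **Drift in the predictors is assumed.** The protocol's timing statements concern pain symptoms. They do not say that thresholds, catastrophizing, PHQ-9 or resilience change between months 1 and 4. Baseline neuropathic pain is not a predictor in Hypotheses 2a to 2c.
- **Confounding through injury severity is not established.** Section 3 says studies relating severity to chronic neuropathic pain have generally been negative.

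These arguments reduce the certainty and the reach of the concern. They do not supply the missing covariate, and the injury-related covariates listed for Hypothesis 1b do not carry over to 2b and 2c.

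**Conclusion.** The point holds in a limited form. From the documents alone, entry can fall anywhere up to four months after injury, visits of the same name can differ by about three months or more in time since injury, and no Aim 2 analysis is stated to account for this. Whether it harms Hypotheses 2b and 2c depends on correlations that the documents do not give. Under the assumed values shown, the effect runs from slight (6.5% false positives, or a power loss of about 5 points) to material (30% false positives, or power of 65%).

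Age and Hispanic/Latino background (2a) do not change over the window and are affected only if they relate to how early a patient enters. The randomized comparison is unaffected, and the outcome is anchored at 12 months post-injury for everyone. A reader might infer that Aim 2 cannot deliver a time-course, or that statements about the whole cohort must begin at month 4. Neither follows. The displays need a stated axis and visible numbers, and month 4 is only the point by which all subjects must be enrolled. The change is worth making because it costs almost nothing.

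**What to change.** **Section 11, Hypotheses 2a, 2b and 2c.** Test 2b and 2c by logistic regression (presence of pain) or linear regression (severity) containing the predictor, TENS group and time from injury to the baseline assessment. A regression form is needed in any case, because chi-square tests, t-tests and simple correlations cannot carry even the TENS covariate already named.

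**Section 11, Data analysis plan.** Index longitudinal displays and summaries by months since injury and show the number prospectively observed at each month. State that sensory-testing and psychological data before about month 4 come only from those already enrolled, and that pain onset before entry is known by recall.

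**Section 7.** Reconcile the anticipated 12 months of enrolment with follow-up that ends 12 months after injury, which gives about 8 to 11 months for entry between four weeks and four months.

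**Cost.** The change is to wording and models. Injury date is already needed for eligibility, so the covariate only requires the baseline assessment date to be held with it. Each model loses one degree of freedom, and the claim about the earliest months becomes slightly narrower.

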- Cognitive dysfunction which limits the ability of the participant to adequately understand procedures and risks.
- Prisoners

- Pregnant Women

Special populations:

- Adults unable to consent: excluded from study
- Individuals -who are not yet adults: individuals who are less than 18 years old will be excluded from the study
- Pregnant women: Women who are known to be pregnant will not be recruited into the study. A pregnancy test will be administered to females prior to enrollment in TENS (or sham) treatment. Women who become pregnant before or during the 8-week TENS treatment period will be discontinued from the study. Women who become pregnant after the 8-week TENS treatment portion of the study will continue to be enrolled, and followed according to protocol guidelines (no information will be collected specifically on the pregnancy or fetus).
- Prisoners: excluded from study
- Neonates: not applicable

5) Number of Subjects*

This is a single-site study and 98 potential participants with newly-acquired spinal cord injuries will be enrolled. See section 22, for more information.

6) Study-Wide Recruitment Methods*

This is not a multi-center study. See section 21.

7) Study Timelines*

It is anticipated that subjects will be enrolled in the study for 12 months (see **Figure 5**, in section 10, below, for procedures timeline).

It is anticipated that enrollment of subjects will occur between November 1, 2016 and January 1, 2022. This enrollment end date is 12-months prior to the end of the funding cycle for this grant, which will allow for complete follow-up of all subjects before study termination.

The estimated date for the investigators to complete this study is October, 2022.

8) Study Endpoints*

The primary study endpoints/outcomes are: 1.) the percentage of subjects who develop chronic neuropathic pain at the 12-month post-spinal cord injury time point (as defined by a score of ≥ 2 on the Spinal Cord Injury Pain Inventory (SCIPI), a self-report scale of symptoms); and 2.) the severity of chronic neuropathic pain (as measured by a self-report rating of neuropathic pain symptoms) measured at the 12-month post-spinal cord injury time point. The secondary study endpoints/outcomes include other aspects of pain symptoms and physical and emotional function. All outcomes and other variables are listed in Table 2 and described in detail below, within the “Procedures Involved” section.

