- The SCI –QOL Resilience scale has been developed and calibrated specifically for those with SCIs¹¹⁷ and is included in follow-up interviews for the SCIMS national database. *This measure will be used for the assessment of resilience as a potential mediating factor for the development and trajectory of pain following SCI [Aim 2].*

vi. Medications:

- While it is not feasible to restrict medication usage throughout the participant's enrollment in a longitudinal study, recording of medications at baseline and changes in medications and dosages across time will be recorded at each study time point as suggested for pain clinical trials.¹¹⁸ *Use of medications traditionally prescribed for analgesic purposes will serve as a secondary outcome measure for the presence and severity of pain⁹² [Aim 1].*

vii. Adverse events:

- Information regarding side effects/ adverse events that are temporally related to the treatment protocol will be collected from all participants. A questionnaire will be administered after all treatment sessions to prompt subjects to report new or increased symptoms and discomfort experienced during the TENS stimulation period. If the subject reports any symptoms, he/she will be asked to indicate the duration of the symptom, the severity, and the associated distress.⁹² These records will be used to address any potential safety concerns and compare the frequency and severity of events across Treatment TENS and Sham TENS groups.

10) Data and Specimen Banking*

No specimens will be collected in this study. Data that is collected on paper will be stored securely in a locked cabinet in a locked office that is accessible only to study staff as described in

section 26: Confidentiality. Electronic data will be collected and stored on a secure server within the University of Miami network, with access limited only to those personnel listed on the IRB application for this study.

11) Data Management*

Power / sample size:

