The PI will assign access to rooms, filing cabinets, and electronic files as necessary for completion of the study.

As this is a single site study, all data will remain on the University of Miami medical school campus, with access under the control of the PI.

12) Provisions to Monitor the Data to Ensure the Safety of Subjects*

Safety endpoints include frequency and severity of adverse events and increased likelihood of developing chronic pain due to TENS treatment. It is anticipated that only infrequent and mild adverse events (e.g., temporary skin irritation from surface electrode adhesive, brief mild pain during initial adjustment of TENS stimulation amplitude) will occur. These events will be handled on an individual basis and may be cause for the PI to discontinue participation of a subject who may be especially sensitive to the study treatment. If these mild adverse events are recorded at higher than expected frequency (i.e., greater than 10% of treatment sessions) or if an unexpected or moderate-severe adverse event occurs, the PI will re-evaluate the treatment parameters and adjust accordingly. All events will be reported to the IRB according to regulations.

Preliminary analyses will be performed after each group of 20 subjects completes the study to determine the efficacy of the treatment by comparing the primary endpoints between the two study groups (TENS and sham TENS). More frequent analyses will be performed if warranted. If these preliminary analyses at any point provide overwhelming support that the experimental intervention (TENS) reduces the development of chronic neuropathic pain or has a substantial clinically meaningful reduction in the severity of chronic neuropathic pain present, then the PI will pursue a change in protocol to provide the active TENS treatment to all available participants. Conversely, if the preliminary analyses reveal that the active TENS treatment puts patients at higher risk for pain or other undesirable outcomes, the PI will seek to terminate the intervention, but continue follow-up on enrolled participants.

13) Withdrawal of Subjects*

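### The only scheduled by-arm review that can end TENS for harm waits for 12-month completers, although earlier pain data are already collected

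*Combined protocol and SAP*

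**What the plan says.** Sections 8 and 12 both state the safety endpoints: "Safety endpoints include frequency and severity of adverse events and increased likelihood of developing chronic pain due to TENS treatment". Section 12 then schedules the interim comparisons: "Preliminary analyses will be performed after each group of 20 subjects completes the study to determine the efficacy of the treatment". They contrast the primary endpoints between TENS and sham. Both primary endpoints are 12-month outcomes; the first, in section 8, is "the percentage of subjects who develop chronic neuropathic pain at the 12-month post-spinal cord injury time point". The harm action hangs on the same looks: "if the preliminary analyses reveal that the active TENS treatment puts patients at higher risk for pain or other undesirable outcomes", the investigator is to seek to end the intervention while follow-up continues. One sentence allows extra looks: "More frequent analyses will be performed if warranted". It gives no trigger or schedule.

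Other safety provisions exist.

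- Section 9, Adverse events: a questionnaire after every treatment session, with the records used to "compare the frequency and severity of events across Treatment TENS and Sham TENS groups". No timing is given.
- Section 12: the investigator re-evaluates the treatment parameters if mild events exceed 10% of sessions, or if an unexpected or moderate-severe event occurs. This is not described as by arm.
- Section 13: withdrawal rules for individual subjects.
- Section 9, Assessment procedures: pain NRS and NPSI before and after each session, with the reason stated: "Collection of this information is important in order to insure that TENS is not related to any increase in pain symptoms during treatment". No by-arm review of these ratings is described.
- Section 9 and Table 2: SCIPI and NPSI also at week 4, at the end of treatment, and at monthly calls until 12 months after injury.

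**The concern.** A harm review protects subjects only if it can act while some are still to be treated. Here the scheduled by-arm review counts people who have finished follow-up, not people who have been exposed, so it trails exposure by most of a year.

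The other provisions do not fill that gap for pain. The adverse-event questionnaire concerns symptoms during stimulation, and Table 2 marks adverse events only at treatment sessions, so pain that emerges afterwards may never be recorded as an event. The investigator and the pain evaluators are blinded (section 9), and section 11 expects 60% of sham subjects to have neuropathic pain at 12 months. Worsening in individuals or in pooled data therefore cannot be attributed to TENS; that takes a by-arm table. No earlier one is scheduled, so it is unclear what would show that extra looks on pain are warranted.

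At stake is how soon harm is detected. The error rate of a benefit claim is a separate matter.

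**Working it through.** **Inputs from the plan.** 98 enrolled, 15% drop-out, about 82 completers (section 11). Recruitment over five years, 60 months (section 22). Treatment starting within four months of injury, with four weeks as the target, and lasting 8 weeks, taken as 2 months (section 9). Endpoint at 12 months after injury (section 8). Allocation 1:1 in blocks of eight (section 9).

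**Assumptions not in the plan.** Uniform accrual; treatment starts at enrolment; drop-outs count as having finished treatment; drop-out between 0 and 15%.

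**1. The plan's own figure.** 98 × 0.85 = 83.3, against about 82 stated: close enough. The plan gives no calendar time for any look.

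**2. Lag per subject.** Treatment starts 1–4 months after injury, so completion comes F = 12 − 4 = 8 to 12 − 1 = 11 months later. Less 2 months of treatment, that leaves 6–9 months after the last session.

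**3. Timing of the looks.** Accrual rate r = 98/60 = 1.633 per month. The look at k completers falls at t = k / [(1 − d) × r] + F, with drop-out d. Subjects past treatment = r × (t − 2), at most 98.

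- k = 20, d = 0, F = 8: t = 12.2 + 8 = 20.2 months; past treatment 29.8.
- k = 20, d = 0.15, F = 11: t = 14.4 + 11 = 25.4 months; past treatment 38.2.

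| Look | Completers | Month | Past treatment | Not yet finished |
|---|---|---|---|---|
| 1 | 20 | 20.2–25.4 | 29.8–38.2 | 59.8–68.2 |
| 2 | 40 | 32.5–39.8 | 49.8–61.8 | 36.2–48.2 |
| 3 | 60 | 44.7–54.2 | 69.8–85.3 | 12.7–28.2 |
| 4 | 80 | 57.0–68.6 | 89.8–98 | 0–8.2 |

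Half of the 29.8–38.2 at look 1, about 15–19, are on TENS.

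**4. Sensitivity.** With retention of 82/98, the upper count past treatment at look 1 is 38.6 and the lower count not yet finished at look 3 is 11.6, about 12. With the section 7 enrolment dates (62 months), look 1 has 29.5–38.1 past treatment across all these retention values. If completing means 12 months in the study, as section 7 can be read, look 1 has 36–40. Drop-out during treatment would lower the counts.

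**5. A treatment-based trigger.** Twenty subjects finish treatment at 20/1.633 + 2 = 14.2 months, when 20 + 2 × 1.633 = 23.3 are enrolled. About 10 of the 20 are on TENS. That is 6–11 months sooner than look 1, with about 5–9 fewer subjects treated on TENS.

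**6. Precision.** With ten per arm and the plan's 60% rate in both, the 95% half-width for a difference is 1.96 × √(2 × 0.6 × 0.4 / 10) = 0.43. Look 1 as planned, with 20 completers, has the same limit.

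**The case against.** A reader might infer that this is the only by-arm harm review planned, or that no pain signal is examined until 30–38 subjects have been treated. The documents support neither. Section 9 plans a by-arm adverse-event comparison, though without timing. Pain is rated at every session for a stated safety purpose, section 12 has a running adverse-event trigger, and section 13 covers withdrawal. What waits is the scheduled by-arm comparison of pain.

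Further points on the other side:

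- Part of the lag belongs to the endpoint. Section 3 defines chronic pain as lasting three months or more and says neuropathic pain often appears some months after injury. Section 9 expects most session ratings to be zero. An early table may show little. This stands for the session ratings, less so for the monthly SCIPI and NPSI.
- Among subjects enrolled, the share already treated barely changes: 29.8/33.1 = 90% to 38.2/41.5 = 92% at look 1, against 20/23.3 = 86% under the earlier trigger. This stands; the gain lies in months and numbers exposed.
- Looks 2 and 3 fall while many are still to be treated, and look 4, at 80 of about 82 completers, is almost the final analysis. This stands, so stressing only the first and last looks would mislead.
- This version is dated 18 July 2022, and section 7 ends enrolment on 1 January 2022. Four months to start plus 8 weeks of treatment takes the last subject to about the end of June 2022. If enrolment closed on schedule, the change protects nobody prospectively.
- By-arm tables on subjects still reporting their own pain put blinding at some risk. This stands and has to be handled in the fix.

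**Conclusion.** The point holds as a worthwhile, cheap improvement; no contradiction between passages is shown. The completer-based trigger itself causes the delay. A named safety endpoint is compared by arm on schedule only 6–9 months or more after each subject's exposure, while earlier pain data have no scheduled by-arm use.

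In size, the first scheduled comparison comes at about month 20–25 rather than month 14, with about 15–19 rather than 10 subjects treated on TENS. These counts rest on the assumptions listed in the check, above all even accrual and treatment starting at enrolment. The lag of 6–9 months does not depend on the accrual pattern. It would be wrong to conclude that subjects go unmonitored during treatment, or that an early table would reliably detect harm.

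**What to change.** Keep the 12-month looks. Add to section 12 a by-arm harm tabulation of all subjects randomised to date, triggered each time 20 subjects finish the 8-week treatment. Tabulate:

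- change in NRS and NPSI from before to after each session;
- SCIPI and NPSI at week 4, at the end of treatment and at each monthly call;
- adverse events.

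State that this review can lead only to the harm action already in section 12 and never to a benefit claim. State also that the tables are prepared by someone already unblinded, or with coded arms, so that the investigator and the pain evaluators stay blinded as section 9 requires.

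The cost is a short amendment and a few tables, with no new visits or data. The drawbacks are slightly more unblinded tabulation, a first review that can show only large differences, and little prospective gain if enrolment has closed as planned.
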